9.7.2.1 Primary objective: Incidence of symptomatic hyponatraemia

The incidence rate of the primary outcome reported since index date in the study observation period will be modelled using a Poisson regression model and expressed as number of cases per 1000 patients-years at risk (+95% CI) for the NOCDURNA group and the LUTS contextual cohort, separately. Person-period at risk is defined according to person-time observed from the index date to the first right censoring event. The numerator will comprise of reports of incident symptomatic hyponatraemia during the observation period. The model will be adjusted for relevant strong risk factors (gender, age (<65, 65-74, \geq 75 years). Stratum-specific incidence rates will also be examined. These will be detailed in the SAP.

As in Phase III pivotal clinical trials incidence of hyponatremia is observed to be higher in the first month of treatment with NOCDURNA than in the subsequent months, two separate Poisson regression models will be applied: (1) including only the first month after the index date, and (2) including only subsequent months after the index date (month 2 and onwards). Recurrent events of hyponatremia are not expected in NOCDURNA patients, as treatment should be discontinued after symptomatic hyponatremia has been diagnosed. For both the NOCDURNA and the LUTS group incidence rates (number of events/ 1000 person-years) will be estimated with 95% CIs.

To investigate how the hazard of hyponatremia more precisely develops in time, hazard functions, based on Cox regression models for time to first event since index date (using the same regressors as in the Poisson model) will be plotted as a function of time.

If, however unlikely, recurrent events have been observed, a Cox model for recurrent events may be applied which will be detailed in the SAP.

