10.1.2 Incidence of symptomatic hyponatraemia

The incidence rate of the primary outcome reported since index date in the study period will be modelled using a Poisson regression model and expressed as number of cases per 1000 patientsyears at risk (+- 95% CI) for the Nocdurna ® group and the LUTS contextual cohort, separately. Person-period at risk is defined according to person-time observed from the index date to the first right censoring event. The dependent variable will be number of events for each person and the independent variable will be treatment, age class, and gender. Stratum-specific incidence rates will also be examined giving rates divided by gender, first month after index date and events occurring after the first month after the index date. Also incidence rates for patients with an age above or equal to 65 years will be calculated. If the model does not converge/modelling assumptions are not met, only unadjusted rates will be presented. This gives the following high level table shell.

Table 4. Thgh level of	uipui uesenj		r ofsson regie	551011		
	Nocdurna	R		LUTS		
	All	Male	Female	All patients	Male	Female
	patients					
All events	X (x-x)	X (x-x)	X (x-x)	X (x-x)	X (x-x)	X (x-x)
First month	X (x-x)	X (x-x)	X (x-x)	X (x-x)	X (x-x)	X (x-x)
After first months	X (x-x)	X (x-x)	X (x-x)	X (x-x)	X (x-x)	X (x-x)
≥ 65 y, All events	X (x-x)	X (x-x)	X (x-x)	X (x-x)	X (x-x)	X (x-x)

Table 4. High level output description of the Poisson regression

A complete table is shown in Table 9

A SAS macro for doing the above analysis has been developed and is described and attached in section 16.2 of this report. The analysis of events during the first month will limit the exposure time to a maximum of 30 days, while the analysis of events after the first month will subtract 30 days for the exposure time. However, there will also be patients that are enrolled late in the study e.g. in the month of December and these patients will have an exposure time of less than 30 days. It must be noted that the analysis of events after the first month is having an immortal time bias, but this bias is expected to be small, since (hopefully) very few patients will die or emigrate during the first month.

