%NOCDURNA_MAC(baseline=baseline,eventdata=eventdata,compare=LUTS,out_table=out_tabl e,dir=dir,ttitle=ttitle);

The 'LUTS' value in the macro can be changed to e.g. 'Off label' when objective 9 is analysed. Please check that the columns are in the correct order in the output and not interchanged.

The SAS macro variable 'DIR' gives a reference to the directory where the RTF table is written, in the development case, the 'C:\temp' directory have been specified, but each site will have a designated directory for the output. Please observe that there is no ending '\' in this macro variable.

The last SAS macro variable 'TTITLE' gives both the headline of the table and the headline (title) of the figure generated inside the SAS macro. Please do not use any ',' inside the text string specified in the macro call.

That is all for the input datasets.

Calculations inside the macro.

The Poisson regression is performed and a calculation is used to calculate the yearly rates. This is the key analysis.

```
ods output ParameterEstimates=ParameterEstimates;
proc genmod data=to_poisson;
class class gender age_class;
model events = class age_class gender / dist=poisson link=log
offset=log_exposure scale=d type3;
store p1;
run;
ods output lsmeans=lsmeans;
proc plm source = p1;
  lsmeans class /ilink cl;
run;
quit;
```

The 'STORE P1' is generating data that can be used for post analysis calculations, in this case will the 'PROC PLM' use the 'P1' data collection.

After the yearly rate per 1000 patient years are calculated and merged together with the rest of the analysis and a 'PROC REPORT' is used for writing the output RTF file.

When the macro is run several time, be sure to exit the Word document between different runs of the SAS macro, if not the output file will be locked and SAS will not be able to write to the file.

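### The reported primary incidence rate is an equal-weight least-squares mean with undisclosed weights, from a model shared with LUTS, so it is not the rate among treated patients

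*Protocol*

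**What the plan says.** SAP section 16.1 gives the code for the macro NOCDURNA_MAC and states its role: "The Poisson regression is performed and a calculation is used to calculate the yearly rates. This is the key analysis". The model line is "model events = class age_class gender / dist=poisson link=log", with log exposure as offset, where the class variable is the cohort. The rate is then taken from "lsmeans class /ilink cl", with no observed-margins (OM) or AT option. The same macro serves the primary objective and secondary objectives 2, 3, 4, 5a, 5b, 6, 8 and 9.

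SAP section 10.1.2 says "The dependent variable will be number of events for each person and the independent variable will be treatment, age class, and gender", yet in the same paragraph wants the rate for the NOCDURNA "group and the LUTS contextual cohort, separately". Protocol section 9.7.2.1 wants it "for the NOCDURNA group and the LUTS contextual cohort, separately" and prespecifies an adjustment: "The model will be adjusted for relevant strong risk factors (gender, age" in three classes. Protocol section 9.7.2.9 and SAP section 10.2.8 bring treatment group in as an extra factor for the comparative analysis only. SAP section 13, which lists changes from the protocol, does not mention a pooled primary model.

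No section names a reference population for the adjusted rate. Tables 4 and 60 show one rate with a confidence interval. Table 9 gives the unadjusted rate no interval, so the rate in Tables 4 and 60 must be the model-based one.

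**The concern.** The primary objective is descriptive: how often symptomatic hyponatraemia occurs in patients who take NOCDURNA, overall and at age 65 and over. A reader will take the row labelled as the incidence rate to be that quantity. It is instead the exponential of an unweighted average of log rates over six age-sex cells, in a population with one third in each age class and half in each sex. Its age and sex effects are common to both cohorts. The plan expects about 2650 + 2610 + 1830 = 7090 NOCDURNA patients (protocol section 9.5.3) and about 300,000 LUTS patients (SAP section 3.1.2.1), so the shared effects will essentially be those of LUTS.

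The figure then feeds the cross-country combination in SAP section 10.4 and Table 60. If a model fails to converge, SAP sections 2.1.1, 10.1.2 and 16.1 substitute the unadjusted rate, so countries could contribute different quantities to one pooled number.

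**Working it through.** 1. **Reproducing the shell.** Table 9 (simulated data), all exposure time, per 1000 person-years. For NOCDURNA the reported rates are 861.40 overall, 1073.58 in men and 688.70 in women. Events are 493 (367 men, 126 women) and person-years 510.4 (335.7 and 174.7).
   - Equal-weight log-scale mean over the sexes: √(1073.58 × 688.70) = 859.9, within 0.2% of 861.40. The match is approximate because the sex columns come from separate fits.
   - Events over person-years: 1000 × 493/510.4 = 965.9. The reported value is 10.8% lower.
   - LUTS: √(662.92 × 427.68) = 532.5 against 532.61 reported; 1000 × 129/219.5 = 587.7, so the reported value is 9.4% lower.
   - Six columns share three scale values, one per model, which confirms that the two cohorts are fitted together.

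2. **Where the shell gap comes from.** Weighting the sex-specific rates by person-years gives (1073.58 × 335.7 + 688.70 × 174.7)/510.4 = 941.8. Of the gap 965.9 − 861.4 = 104.5, the part 941.8 − 861.4 = 80.4 (77%) is sex weighting; men hold 335.7/510.4 = 66% of person-time. Within sex the gap is small: 1073.6 against 1000 × 367/335.7 = 1093.2 in men (1.8%), and 688.7 against 1000 × 126/174.7 = 721.2 in women (4.5%).

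3. **General form.** In a log-link Poisson model with a cohort term, fitted and observed events agree within each cohort. Hence LS-mean/crude = exp(mean age effect + mean sex effect) ÷ Σ[person-time share × exp(age effect + sex effect)].

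4. **Range for age.** The documents give neither age shares nor age rate ratios, so both are assumed, with no sex effect. Example: shares 20/35/45% and ratios 1:2:4 give (1×2×4)^(1/3) ÷ (0.2 + 0.7 + 1.8) = 2/2.7 = 0.74.

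| Share <65 / 65–74 / ≥75 | 1:1.5:2 | 1:2:4 | 1:3:6 |
|---|---|---|---|
| 20/35/45% | 0.89 | 0.74 | 0.66 |
| 30/35/35% | 0.95 | 0.83 | 0.76 |
| equal thirds | 0.96 | 0.86 | 0.79 |
| 40/35/25% | 1.01 | 0.95 | 0.89 |
| 60/25/15% | 1.13 | 1.18 | 1.16 |

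   A still older mix (15/35/50%, ratios 1:3:6) gives 0.62. The equal-thirds row shows that correct weights alone do not cure the problem, because a log-scale mean lies below the arithmetic mean.

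5. **Range for sex.** Also assumed, with no age effect: 67% women with a female/male ratio of 1.28 gives 0.95; 67% men with a male/female ratio of 0.6 gives 1.06.

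6. **Effect of pooling.** Assume 10,000 NOCDURNA and 400,000 LUTS person-years, NOCDURNA shares 20/35/45% with ratios 1:2:4, and LUTS shares 30/35/35%. Changing only the LUTS ratios from 1:2:4 to 1:3:8 moves the NOCDURNA LS-mean from 10.0 to 8.1 per 1000, while its crude rate stays at 13.5.

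**The case against.** The protocol prespecifies an adjusted rate, and a common reference population suits a side-by-side display of the two cohorts. Replacing it by the crude rate alone would drop something planned. That stands, and the fix keeps an adjusted rate. It does not excuse leaving the reference population unstated.

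Asking for rates separately could mean only that each is expressed per cohort, and SAP section 10.1.2 openly lists treatment as a covariate. But protocol section 9.7.2.9 introduces treatment as a new factor at the comparative stage, which implies that the primary model lacks it. At the least the two documents conflict.

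A reader might infer that the reported rate always understates, by over-weighting patients under 65. The documents do not support this. Equal weights already put two thirds on patients aged 65 and over. In the Table 9 shell 2435/3512 = 69% of subjects are that old, so age weighting matters little there.

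Nor can the shell supply a magnitude. It is simulated, LUTS is the smaller group in it, and its first-month block has 491.4 person-years for 3512 subjects when a 30-day cap allows about 3512 × 30/365.25 = 288. Table 1A of SAP Amendment 1 is labelled as random numbers and should not be cited.

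Table 9 does print events, person-years and an unadjusted rate, so a reader can divide. But that rate has no interval, and its shell value for NOCDURNA, 1201.8, is not 965.9.

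**Conclusion.** The point holds on the mechanism, which follows from the code. The headline rate is a log-scale average with equal weights for age class and sex, nowhere disclosed, using effects that NOCDURNA is forced to share with a far larger LUTS cohort. It is not the rate among treated patients. The equal weighting carries over to every objective that uses the macro. The sharing with LUTS does not extend to objectives 8 and 9, which contain NOCDURNA patients only; in objective 9 the two label groups share effects instead.

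The direction is conditional. The age component understates if risk rises with age, as protocol section 7 indicates for patients aged 65 and over, and if the cohort is at least as old as equal thirds. It can overstate in a cohort mostly under 65. Over the tabulated assumptions LS-mean/crude runs from 0.66 to 1.18, and sex weighting can push either way. The 10.8% shortfall in the Table 9 shell shows the mechanism and is not an estimate of the error to expect.

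**What to change.** - For each cohort, and for each stratum shown, report events divided by total person-years with an exact Poisson 95% interval as the descriptive rate. Correct the unadjusted row of Table 9 so that it equals this.
- Keep the prespecified age- and sex-adjusted rate, but fit each cohort separately, or add class-by-age and class-by-sex terms. Standardise on the rate scale (average the predicted rates, not their logs) to a stated age-sex person-time distribution, such as the observed NOCDURNA one, used for both cohorts. Adding the OM option alone is not enough, because the averaging would stay on the log scale.
- Label each rate and its reference population in Tables 4, 9 and 60. Combine only like with like across countries.
- Bring SAP section 10.1.2 and the macro into line with protocol section 9.7.2.1, or record the departure in SAP section 13.

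Cost: slightly more programming in the macro and one more row with an interval in the tables. No new data are needed.

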16.2 Another macro

A macro is also developed for doing the analysis in objective 7 comparing the incidence rate ratios between the treatments (Nocdurna ® and LUTS) taking confounding factors into the analysis. The confounding factors are age class and gender.

That macro is called NOCDURNA_MAC7 (the 7 reflecting objective 7) and has the basic data flow and the same input datasets. Once the datasets for the Poisson regression are created this macro just needs to be called for doing the analysis described in objective 7. This macro should not be used for analysing objective 9.

16.3 **Programming left to be done for analysing outcome**

A program for study objective 2 with descriptive analysis of baseline characteristics has not been developed. It is expected that the institutions already are have standard software for this analysis adapted to the variable names and values in the databases.

The SAS boxplots, symmetry plots, normal quantile plots and normal probability plots also need to be generated. The PLOT statement in PROC UNIVARIATE will generate the Boxplot. The normal probability plots will be generated with PROBPLOT statement in PROC UNIVARIATE. The PROC UNIVARIATE with a QQPLOT statement will generate the normal quantile plots. Finally, the symmetry plot will be generated by the HISTOGRAM / NORMAL statement in PROC UNIVARIATE. The final appearance of the figures will depend on the actual data and the axe are difficult to determinate before the first interim analysis. Examples of some of these figures can be found in the SAS PROC UNIVARIATE documentation and in (Dennis et al., 2019)

The Cox regression is not included. Please add the 'PLOTS=SURVIVAL' and a 'CLASS treatment group' to the SAS statement in the 'PROC PHREG' procedure.

Also the COX regression used in the case if more than 5% of the patients are having more than 1 event are not included, but there is a reference in the SAS example. SAS code for generating **Figure 31** will be provided by Statistician **PPD**.

16.4 Meta-analysis

In the final report planned for December 2023 a meta-analysis will be done. The meta-analysis is planned for Q3 in 2023. Combining incidence rates and descriptive statistics are described in the text, but the programming meta-analysis of the incidence rate ratios is described below.

A suite of SAS macros have been developed to do this task sponsored by Novartis. These macros will be applied.

Table 69. Description of SAS macros used for meta-analysis

Macro name	Description	Link
Mabinary	To carry out various approaches to analyzing binary data including classic Mantel-Haenszel analysis but also, for example, the analysis of Normal-binomial mixtures using PROC NLMIXED	mabinary.sas
maforest	To produce so-called forest plots whereby individual trials are represented by horizontal lines joining lower and upper confidence limits with a plotting symbol for the estimate and a final line and symbol for the overall meta-analytic summary	maforest.sas
mafunnel	To produce funnel plots. These plot the treatment estimate on the horizontal axis and the reciprocal of the standard error of the treatment estimate on the vertical axis.	mafunnel.sas
magalbraith	To produce radial or Galbraith plots as described in Statistics in Medicine , 1988.7,889-894. These plot the Z-scores, that is to say the ratio of estimated treatment effect to standard error, against the reciprocal of the standard error, where the latter is calculated as for a fixed effects analysis.	magalbraith.sas
mainverse	To carry out classic fixed effects meta-analysis using inverse weighting by variances of treatment contrasts.	mainverse.sas
mapeterlee	To implement Lee's checks as described in Statistics in Medicine ,1999, 18 ,1973-1981.	mapeterlee.sas
maqq	To produce QQ plots of estimated treatment effects by trial.	maqq.sas
marandom	To carry out random effects analysis using the approach of DerSimonian and Laird (DSL), Controlled Clinical Trials , 1986,7,177- 188 and also using that of Hardy and Thompson(HT), Statistics in Medicine , 1996, 15 , 619-629.	marandom.sas
masensitivity	To examine the sensitivity of conclusions from random effects analysis to the magnitude of the random effects variance.	masensitivity.sas

There is also a sample program for showing the correct usage of the macros.

16.5 ICD 10 and ATC codes used in the study

Definitions of the LUTS cohort, outcome events and covariates

Table 70. ATC codes used to define the LUTS cohort					
Characteristic ATC code Description					
Overactive bladder	G04BD	Drugs for urinary frequency and incontinence			
Benign prostatic hyperplasia G04C Drugs used in benign prostatic hypertrophy					
Copied from protocol					

Table 71. Codes used to define subpopulations, e.g. the contraindications for Nocdurna ® usage.

ICD-10 code	Description
E87.1	
R63.1	
150	Heart failure (all subcodes included)
N18.3	Chronic kidney disease, stage 3 (moderate)
N18.4	Chronic kidney disease, stage 4 (severe)
N18.5	Chronic kidney disease, stage 5
N18.6	End stage renal disease
E22.2	
	code E87.1 R63.1 I50 N18.3 N18.4 N18.5 N18.6

Table 72. Codes used to define outcome events

Outcome	ICD-10 code	Description
Hyponatremia		
Hyponatraemia	E87.1	
Hyponatremia	n/a	Will be ascertained using biochemical definition:
(biochemical definition)		serum sodium concentration <135 mmol/L (mild
		hyponatraemia)
		Evaluated only in Denmark
Major cardiovascular even	nts (MACE)	
Myocardial infarction	I21, I22	
Stroke, ischemic	I63.3-I63.9,	
	I66	
Major venous thromboem	bolic events	
Pulmonary embolism	I26	
Deep vein thrombosis	I80.1–I80.9	
Portal vein thrombosis	I81	
Mortality		
All-cause mortality	Any	Death from any cause
Heart failure		
Heart failure	150	
Copied from protocol		

Covariate	ICD-10 code	ATC code	Description/comment
Comorbidities			
History of hyponatraemia,	Please refer to		
MACE and VTE	Table 72		
Polyuria	R35		Polyuria
Diabetes mellitus	E10		Type 1 diabetes mellitus
	E11		Type 2 diabetes mellitus
	E12		Malnutrition-related diabetes mellitus
	E13		Other specified diabetes mellitus
	E14		Unspecified diabetes mellitus
Diabetes insipidus	E23.2		•
Overactive bladder	N31.0		Uninhibited neuropathic
			bladder, not elsewhere classified
	N31.2		Flaccid neuropathic bladder, not elsewhere classified
	N31.9		Neuromuscular dysfunction o bladder, unspecified
	N39.4		Other specified urinary incontinence
	R39.1		Other difficulties with micturition
		G04BD	Drugs for urinary frequency and incontinence
Benign prostatic hyperplasia	N40		Benign prostatic hyperplasia
Demgn prostatie nyperplasta	D29.1		Benign neoplasm of prostate
	D2).1	G04C	Drugs used in benign prostation hypertrophy
Urinary tract infection	N39.0		Urinary tract infection, site not specified
	N120		Cystitis
	N30		2
	N10		Acute tubulo-interstitial nephritis
Polydipsia	R36.1		Excessive thirst
Heart failure	I50		EACCSSIVE HIISt
	130 I10		Essential (primary)
Hypertension	110		Essential (primary)
			hypertension; medications to

Table 73. Codes used to define covariates

Hyperlipidaemia	E78		be used as proxy (see below under co-medications) Disorders of lipoprotein metabolism and other lipidaemias; medications to be used as proxy (see below under co-medications)
Atrial fibrillation	I48		
Obesity	E66		
Kidney disease	N18		
	N19		
Cystic fibrosis	E84		
Pre-eclampsia	011		Pre-eclampsia superimposed on chronic hypertension
	O14		Pre-eclampsia
Chronic lung disease	J40-J47		Chronic lower respiratory diseases
	J60-J70		Lung diseases due to external agents
	J80		Adult respiratory distress syndrome
	J82		Pulmonary eosinophilia, not elsewhere classified
	J84		Other interstitial pulmonary diseases
	J95-J99		Other diseases of the respiratory system
Liver disease	K70-K77		Diseases of liver
	F10	N07BB	F10 (mental and behavioural disorders due to use of alcohol) and N07BB (drugs used in alcohol dependence) included as proxy measures of liver disease
Cancer	C00-C43 C45-C97		Cancer excluding non- melanoma skin cancer C61 (prostate cancer) and C67 (bladder cancer) of special interest
Dementia	F00		Dementia in Alzheimer disease

	F01		Vascular dementia
	F02		Dementia in other diseases
			classified elsewhere
	F03		Unspecified dementia
	F04		Organic amnesic syndrome,
			not induced by alcohol and
	~ • •		other psychoactive substances
	G30		Alzheimer's disease
	G31.0		Frontotemporal dementia
	G31.1		Senile degeneration of the brain
Number of hospitalisations	Any		Marker of overall health; to be
			assessed in the year before the
			index date
Number of emergency room	Any		Marker of overall health; to be
visits			assessed in the year before the
Comedications including days	a that we are in a	hogao the wigh of h	index date
Co-medications, including drug Loperamide	s inai may incr	A07DA03	yponairaemia
Antidiabetics		A07DA03	A10BB (sulfonylureas
/ intiduoenes		1110	including chlorpropamide), of
			special interest
Amiodarone		C01BD01	1
Antihypertensives		C02	
Diuretics		C03	C03A, C03B, C03C, C03D
			and C03E of special interest
Beta blocking agents		C07	C07B, C07C and C07D of
~ · · · · · · · ·		~~~~	special interest
Calcium channel blockers and		C08G	
diuretics			
ACE inhibitors		C09A	C09BA of special interest
Angiotensin II receptor blockers		C09C	
Angiotensin II receptor		C09D	C09DA of special interest
blockers (combinations)		CO9D	CO3DA of special interest
Lipid-modifying agents		C10	
Vasopressin and analogues		H01BA	
(incl. desmopressin)			
Systemic corticosteroids		H02	
Antiepileptics		N03A	N03AF01 (carbamazepine)

and N03AX09 (lamotrigine) of special interest

Non-selective monoamine reuptake inhibitors	N06AA	
Selective serotonin reuptake	N06AB	
inhibitors		
Chlorpromazine	N05AA01	
NSAIDs	M01A	
Opioids	N02A	
Phenothiazines with aliphatic	N05AA	N05AA01 (chlorpromazine)
side-chain		of special interest
Lithium	N05AN01	
Antidepressants	N06A	
Antiinflammatory agents, non-	M01A	
steroids		
Copied from protocol		

STATISTICAL ANALYSIS PLAN AMENDMENT 1

POST AUTHORISATION SAFETY STUDY (PASS), SAP

Post-authorisation safety study of NOCDURNA for the symptomatic treatment of nocturia due to idiopathic nocturnal polyuria: A multi-country cohort study using secondary data

000248

Investigational Product:	Desmopressin, one oral lyophilisate per day
Indication:	N/A
Phase:	IV
Author:	PPD
Date of issue:	11 th of November 2022
Version:	1.0

[figure not shown]
The information in this document is confidential and is proprietary to Ferring Pharmaceuticals A/S or another company within the Ferring Group. It is understood that information in this document shall not be disclosed to any third party, in any form, without prior written consent of an authorised officer of Ferring Pharmaceuticals A/S or another company within the Ferring Group

Version No.	Effective Date	Reason for the Change / Revision	Supersede	
AMENDMENT 1	11 November 2022	EMA has required one additional sensitivity analysis to be performed included in the next reports.	N/A	

Review and Approval of Amendment to Statistical Analysis Plan

Reviewers:

Approval by (e-signed in REAL):

TABLE OF CONTENTS

1	INTRODUCTION	5
2	REASON FOR ADMENDMENT	6
3	ANALYSIS SET	7
4	ADDITIONAL SENSITIVITY ANALYSIS	8
5	TABLE SHELL	9

List of Tables

Table 1A extra	Sensitivity analysis. High level results of Incidence of symptomatic hyponatraemia	
	in country	9
Table 2A extra	Sensitivity analysis. Incidence of symptomatic hyponatraemia in country	9

